2.0 Background/Scientific Rationale

Tissue ischemia is one of the main etiologies of pressure injury.¹ It is inevitable during bed-ridden and wheelchair bound conditions, such as spinal cord injury (SCI), or prolonged surgery procedure in the operating room. Active alternating pressure (AP) mattresses are covered by Medicare policy for patients with multiple/large stage 2/ stage 3 pressure injuries to relief interface pressure and prevent recurrence of pressure injuries.² Previous studies demonstrated that the protective mechanisms of AP on pressure injury include redistribution of surface pressure, and allowing more blood supplies while lying on the support surface.³⁻⁵ The Dabir AP overlay (DabirAIR™, Dabir Surfaces Inc., Hardwood Heights, IL) is low profile yet possesses similar characteristics as other AP mattresses on the market; it is intended for clinical use, such as operation room (OR) where AP mattresses may not be an option. We expect Dabir AP overlay will be beneficial to people at risk of pressure injury by maintaining the blood supply during weight bearing condition.

In addition to pressure redistribution and increasing blood supplies, we also postulate that the if an AP overlay will be beneficial to the weight-bearing skin by means of preconditioning the skin with short-term ischemia, i.e. when air cells inflate. Ischemic preconditioning is a method used to prevent tissue damage caused by ischemic events, such as stroke and myocardial infarction,⁶ by means of slowing down ATP depletion in the short-term subsequent ischemic episodes and washing out the harmful catabolites during each short-term period of reperfusion. Recently, this method is implemented to heal diabetic foot ulcer by remotely precondition the lower limb.⁷ We hypothesize that the alternating pressure characteristics of the Dabir AP overlay could be utilized as a method for preconditioning to protect weight-bearing tissue in people with SCI.

To quantify the severity of tissue ischemia, we will collect the non-invasive reactive hyperemic response as an outcome. Reactive hyperemia is characterized by sudden increase in blood flow after temporary obstruction of the blood flow. Previous studies used this response to simulate the tissue response toward ischemia in people that are at risk of pressure ulcer, such as spinal cord injury.^{8,9}

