3.0 Objectives/Aims

The objective of this study is to evaluate the protective mechanisms of Dabir AP overlay on weight bearing tissue of people with chronic spinal cord injury (SCI). Our central hypothesis is that the Dabir AP overlay will cause lower amount of interface pressure and allow more skin blood flow during weight bearing as compared to regular OR overlay. In addition, people with SCI will have better tolerance to prolonged weight bearing after preconditioned with the Dabir AP overlay.

There are three aims (with related hypotheses) for this study:

Aim 1: To determine the effectiveness of pressure redistribution with Dabir AP overlay.

Hypothesis 1. Our participants will demonstrate lower interface pressure at sacrum and heel when lying supine for 40 minutes on Dabir AP overlay as compared to that on regular OR overlay (AliMed®).

Aim 2: To examine the severity of tissue ischemia with the use of Dabir AP overlay.

Hypothesis 2a. Our participants will demonstrate greater skin blood flow at sacrum and heel when lying supine for 40 minutes on Dabir AP overlay as compared to that on regular OR overlay.

Hypothesis 1b. Our participants will demonstrate smaller reactive hyperemic response at sacrum and heel after being relieved from 40 minutes of lying supine on Dabir AP overlay as compared to that on regular OR overlay.

Aim 3: To assess the feasibility of utilizing Dabir AP overlay for ischemic preconditioning for prolonged weight bearing condition.

Hypothesis 3. With 40 minutes of preconditioning using the Dabir AP overlay, our participants will demonstrate smaller reactive hyperemic response at sacrum and heel after being relieved from the regular OR overlay as compared to that without preconditioning.

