9.0 Data Analysis

The MatLab program (The MathWorks Natick, MA) will be used to process the skin blood flow signal. The signals will be analyzed with two signal processing methods to characterize the responses in both time and frequency domains. Details of both methods were published previously by the PI.¹⁴

1) *Exponential curve-fitting technique:*

To select the time-domain parameters of the reactive hyperemia and heat hyperemia objectively. A tenth ordered Chebyshev I low pass filter (with cut off frequency at 0.15 Hz) will be applied to remove the noise caused by respiration and cardiac movement.¹⁰ We will use a least squares model to fit the filtered reactive and heat hyperemic curves, and all parameters (including peak, time to peak, area under curve of reactive hyperemia; and first peak, second peak and time to first and second peaks, area under curve of heat hyperemia) will be derived from the fit curves.

2) *Time-frequency analysis:*

To further examine the different control mechanisms of SBF by decomposing the signal in frequency domain. Short-time Fourier transform will be used to decompose the signal by breaking the signal into short-time segments (windows), then computed Fourier analysis within each segment to calculate

spectral densities. A 256-sample Hanning window (512 seconds) will be used to compute the spectrogram.

Please see section 12.0 for details of all statistical analyses.

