12.0 Statistical Considerations

For aims 1 and 2, paired *t*-tests will be computed to compare the interface pressure and skin blood flow during 40 minutes of AP overlay (AP protocol) vs. OR overlay (Ctrl protocol). Paired *t*-tests will also be used to compare the reactive hyperemic response during RH1 (AP protocol) vs. RH (Ctrl protocol). For aim 3, paired *t*-tests will be computed to compare the skin blood flow during OR overlay (AP protocol) vs. OR overlay (Ctrl protocol), and the reactive hyperemic response during RH2 (AP protocol) vs. RH (Ctrl protocol). SPSS will be used for all statistical analyses. Since this is a pilot study, we will test the study on 15 subjects. Results from this study will be used to calculate sample size for future studies. In case of dropout or subject decease during this study, we propose to recruit up to 20 subjects for this study.

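### Must the plan fix one hyperaemia parameter, a site rule and a significance level before Hypotheses 1b and 3 can be judged?

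*Combined protocol and SAP*

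**What the plan says.** Section 2.0 gives the purpose of the measure: "To quantify the severity of tissue ischemia, we will collect the non-invasive reactive hyperemic response as an outcome". Section 3.0 then makes two directional predictions. Hypothesis 1b, printed under Aim 2 and presumably meant as 2b, is "Our participants will demonstrate smaller reactive hyperemic response at sacrum and heel after being relieved from 40 minutes" on the AP overlay. Hypothesis 3 is that, after preconditioning, "our participants will demonstrate smaller reactive hyperemic response at sacrum and heel after being relieved from the regular OR overlay", compared with no preconditioning.

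Section 9.0 obtains "all parameters (including peak, time to peak, area under curve of reactive hyperemia" from the fitted curves, adds a time-frequency analysis, and ends with "Please see section 12.0 for details of all statistical analyses". Section 12.0 uses paired t-tests to "compare the reactive hyperemic response during RH1 (AP protocol) vs. RH (Ctrl protocol") and, for Aim 3, to compare "the reactive hyperemic response during RH2 (AP protocol) vs. RH (Ctrl protocol"). It gives no parameter, level or sidedness. It calls the study a pilot of 15 subjects and adds: "Results from this study will be used to calculate sample size for future studies".

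**The concern.** Each of the two hypotheses invites a yes or no, and the plan offers at least three parameters at two sites, so at least six candidate tests per hypothesis. The cross-reference to Section 12.0 does not narrow them. A smaller response is a natural description of peak or area and an unclear one of time to peak. The predictions are directional, so a one-sided test is a credible reading alongside the usual two-sided one.

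The problem would remain even with complete reporting: the tables could be full and the verdict on preconditioning still depend on the analyst. A future sample size also has to rest on one measure, and the plan does not say which.

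**Working it through.** **Inputs.** From the plan: 15 subjects and paired t-tests (Section 12.0), three listed hyperaemia parameters (Section 9.0), two sites (Section 6.0). The plan states no level, power, effect size or SD, so it has no figure of its own to reproduce. Assumed: a 5% level; a true standardised paired difference d of 0.5 or 0.8, equal at both sites and for all parameters; correlation between sites 0 to 0.7; correlation between peak and area 0.7 or 0.9. Correlated cases are simulated; independent cases can be checked by hand.

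1. **Thresholds.** With 14 degrees of freedom the critical t is 2.145 two-sided and 1.761 one-sided. Dividing by √15 = 3.873 gives observed standardised differences of 0.554 and 0.455. A result between these passes one test and fails the other.

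2. **False support in the AP direction, two-sided 5%.** Each test contributes 0.025.
   - Both sites, one parameter, independent: 0.025² = 0.0006. At correlation 0.7: 0.0075.
   - Both sites on the same parameter, any of the three: 1 − (1 − 0.000625)³ = 0.0019. At correlation 0.7: 0.0166.
   - Any single one of six tests: 1 − 0.975⁶ = 0.141. At correlation 0.7: 0.085.

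3. **Site rule, one parameter.** Power at one site is 0.438 at d = 0.5 and 0.821 at d = 0.8.
   - Independent sites, d = 0.5: both 0.438² = 0.192; either 1 − 0.562² = 0.684; the readings differ in 0.684 − 0.192 = 0.492.
   - At correlation 0.7, d = 0.5: both 0.305, either 0.568, so they differ in 0.263.
   - At d = 0.8 they differ in 0.293 (independent) to 0.167 (correlation 0.7).

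4. **Peak against area, both sites required.** Share of studies with opposite verdicts, over site correlations 0 to 0.7:

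| Correlation of peak and area | d = 0.5 | d = 0.8 |
|---|---|---|
| 0.9 | 0.122 to 0.139 | 0.130 to 0.157 |
| 0.7 | 0.196 to 0.236 | 0.221 to 0.262 |

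5. **Sidedness, both sites required.** One-sided power at one site at d = 0.5 is 0.578. With independent sites the verdicts differ in 0.578² − 0.438² = 0.334 − 0.192 = 0.142. Across correlations 0 to 0.7 and both effect sizes the range is 0.112 to 0.145.

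6. **Future sizing.** If the true d is 0.5, 34 subjects are needed for 80% power. With one parameter named in advance, a point estimate from 15 subjects still calls for 17 or fewer in 0.235 of pilots, and the 10th to 90th percentiles of the calculated size run from 12 to 277. That spread comes from the size of the pilot and remains after a parameter is named.

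The largest disagreements, in step 3, need an analyst to read the joint wording of the hypotheses as an either-site rule. The 14% error rate in step 2 needs a rule that any one of six tests is enough. The text suggests neither.

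**The case for a change.** The strongest case for a change does not use those readings. With both sites required, parameter and sidedness are still open, and steps 4 and 5 show that each can change the verdict. Pilot status does not remove the point, because Section 12.0 still specifies tests of stated hypotheses. The publication cited in Section 9.0 is cited for signal processing, not for statistical analysis. Closing the gap would take only wording.

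This much stands: the parameter and the level are not written down, and naming them would be tidier. The remedies, however, are choices on which statisticians would differ:

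- Area covers size and duration of the response, but the documents rank it no higher than peak. Area also needs a baseline rule. Section 6.0 collects a baseline only at the start of each protocol, so RH2 follows two loading periods and RH1 without a fresh one. Naming area alone would leave analysts free to compute it differently.
- Requiring two-sided significance at both sites gives 19% to 30% power at d = 0.5. A real effect of that size would be declared unsupported in 70% to 81% of studies, a poor bargain in a pilot.
- Making everything else descriptive would demote the comparison of flow during OR loading, which Section 12.0 plans as an Aim 3 test.
- Sizing the next study on an upper confidence limit for the SD addresses the imprecision in step 6, not the missing parameter.

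**Conclusion.** No change to the plan follows. The omission is one that analysts fill sensibly: test each listed parameter at sacrum and heel with a paired t-test at the conventional two-sided 5% level, read the hypotheses as needing both sites, and show all the results. False support is then 0.2% to 1.7% per hypothesis even if any of the three parameters may carry it.

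The residual ambiguity is modest: 12% to 26% of studies for peak against area, and 11% to 14.5% for sidedness. It affects a supported or not-supported label in a study whose declared use is to size later work and whose third aim concerns feasibility. Where peak and area disagree, showing both tells the reader more than a verdict fixed on one of them.

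This rests on the assumed level, effects and correlations, none of which the documents give, and on every listed parameter being reported at both sites. If only favourable results were shown and any one of six counted, false support would be about 9% to 14%. That would be a reporting fault, and the plan does not propose such a rule.

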6.0 Study Design and Procedures

Study Design. This study uses a repeated measures design, and each subject will act as his/her own control. Each subject will undergo the two protocols in the experimental procedures: AP protocol and Control protocol. To ensure the order of the two protocols are randomized, the order of AP and Control protocols will be determined by drawing one envelope from the envelope pool. We will start with a pool of total 20 envelopes (10 envelopes indicating AP protocol first, and 10 envelopes indicating control protocol first). Once the envelope is drawn from the pool, it will not return to the pool.

Study Procedures (Research purpose). After enrollment, subjects will proceed to the following procedures: 1) experimental procedures, 2) vascular control measures, 3) pressure mapping of wheelchair and 4) blood withdraw.

1) **Experimental procedure (approximately 4.5 hours)**

Each subject will undergo two study protocols: AP and control (figure 1), and the order of the protocols will be randomized as described previously. A 30-minute washout period will be provided in between the two protocols. Two Laser Doppler flowmetry (LDF) flat probes (moor instrument, Wilmington, DE) will be taped to the sacrum and one heel to collect the skin blood flow response throughout both AP and control protocols. A whole body pressure mapping system (Xsensor, Xsensor Technology Corp., Alberta, Canada) will be used between the subject and the overlay to collect the inter pressure data. For the AP cycle, we will use four 10-minute cycles (5 minutes of high pressure and 5 minutes of low pressure).

AP protocol: The subject will first lie on his/her side quietly for 10 minutes to collect the baseline skin blood flow, followed by lying supine on the Dabir AP overlay for 40 minutes, and then side lying for 30 minutes to collect the first reactive hyperemic response. To test the effect of preconditioning, the subject will then lie supine on the OR overlay for 40 minutes followed by side lying for 30 minutes for the second reactive hyperemic response.

Control protocol: The subject will first lie on his/her side quietly for 10 minutes to collect the baseline skin blood flow, followed by lying supine on the OR overlay (AliMed®) for 40 minutes, and then side lying for 30 minutes to collect the reactive hyperemic response for control protocol.

AP	Baseline (10 min)	AP overlay (40 min)	RH 1 (30 min)	OR overlay (40 min)	RH 2 (30 min)

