Ctrl	Baseline (10 min)	OR overlay (40 min)	RH (30 min)		

Figure 1. Illustration of the full course of the experimental protocols: Alternating pressure (AP, top panel) and Control (Ctrl, bottom panel).

2) Vascular control measures (approximately 30 minutes)

The PI, or key personnel will then collect the vascular control measures, including the heat hyperemic (HH) blood flow response, and the skin vasomotor response. A non-invasive combined laser Doppler and white light reflectance spectroscopy (LDF-WLRS) probe (CP2T-1000, Moor Instrument, Wilmington, DE) will be used for both measures.

HH blood flow response will be measured at the sacrum and one heel while the subject is in side-lying position. Figure 2 demonstrates the HH measurement setting. HH will be induced with the heater at the tip of the probe head (41°C for 5 minutes). This HH measure will take approximately 7 minutes (2 min-baseline, 5 min-heating) per location. In total, the HH measures will take up to 15 minutes to complete.

The skin vasomotor response will be induced using cutaneous electrical stimulation (3-10 mA, 0.2-1.0 ms pulses at 20 Hz, 1 s trains) delivered via 1 cm Ag-AgCl surface electrodes applied bilaterally (4 cm apart) to the forehead (above lesion) and the abdominal wall (below lesion) while the subject is in a semi-reclined position.¹² For each site, 5-8 stimuli will be delivered randomly. CP2T-1000 probe will be used to collect SBF and tissue oxygenation data at pulp of the second finger and toe. Subject will be in a semi-reclined position (about 30° from horizontal plane) during this protocol, and it will take up to 15 minutes to complete this protocol.

[figure not shown]

Figure 2. (A) hand held LDF-WLRS probe with heater ring, (B) HH measure.

3) Pressure mapping of wheelchair (approximately 10 minutes)

The subject will be asked to transfer back to his/her wheelchair with the pressure mapping system placed between the wheelchair and the subject to collect the interface pressure data. The pressure mapping system is the same as that used between the subject and overlay to collect the interface pressure data.

4) Blood withdraw (approximately 15 minutes)

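### Does the 512-second spectrogram window need changing because it is longer than the heat-hyperaemia record?

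*Combined protocol and SAP*

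**What the plan says.** Section 9.0 (Data Analysis) introduces the processing of the skin blood flow signal in general terms: "The signals will be analyzed with two signal processing methods to characterize the responses in both time and frequency domains". It then describes two methods and says that details of both are in an earlier publication by the investigator.

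- Method 1 is exponential curve fitting. Its purpose is given as "To select the time-domain parameters of the reactive hyperemia and heat hyperemia objectively". The parameters listed for heat hyperaemia are two peaks, the times to those peaks and the area under the curve.
- Method 2 is time-frequency analysis by short-time Fourier transform. Its purpose is "To further examine the different control mechanisms of SBF by decomposing the signal in frequency domain", and its one numerical setting is "A 256-sample Hanning window (512 seconds) will be used to compute the spectrogram". It does not say which recordings it covers, and it gives no rule for overlap or padding.

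Section 6.0 gives the recording lengths. For heat hyperaemia: "This HH measure will take approximately 7 minutes (2 min-baseline, 5 min-heating) per location", and for the two sites together "In total, the HH measures will take up to 15 minutes to complete". In the main experiment the baseline lasts 10 minutes, each period on an overlay 40 minutes and each reactive-hyperaemia period 30 minutes. The alternating-pressure (AP) overlay runs "four 10-minute cycles (5 minutes of high pressure and 5 minutes of low pressure").

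Section 12.0 plans paired t-tests for interface pressure, skin blood flow and reactive hyperaemia. For load it will "compare the interface pressure and skin blood flow during 40 minutes of AP overlay (AP protocol) vs. OR overlay (Ctrl protocol"). It names no spectral outcome.

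**The concern.** The opening sentence of section 9.0 can be read as sending every signal through both methods. On that reading heat hyperaemia goes into the spectrogram, yet its recording is shorter than a single window. The analyst would have to leave it out, pad it or choose another window, and section 9.0 does not say which. Padding would produce one spectrum mixing the two minutes before heating with the five minutes of heating, with no time resolution, and its content would depend on where the padding was placed.

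A second worry concerns the load periods. Each AP phase lasts 300 seconds, so every 512-second window crosses at least one change of pressure. High and low phases are blurred, and the overlay's own 600-second cycle can put power into the slowest bins of an AP spectrum but not of an operating-room (OR) overlay spectrum. A slow-frequency difference between overlays might then be taken for vascular control when part of it is the pump cycle.

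**Working it through.** **Inputs.** From section 9.0: window 256 samples, 512 s; low-pass cut-off 0.15 Hz (stated for method 1). From section 6.0: heat recording 2 min + 5 min per site, at most 15 min for two sites; baseline 10 min; reactive hyperaemia 30 min; load 40 min; AP phases 5 min.

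**Is the stated window coherent?** Implied sampling rate = 256 / 512 = 0.5 Hz. The highest resolvable frequency is 0.5 / 2 = 0.25 Hz, above the 0.15 Hz cut-off. The bin spacing is 1 / 512 = 0.00195 Hz. No sampling rate is stated, so 512 s cannot be reproduced independently, but nothing in the documents contradicts it.

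**Which recordings hold a full window?** Samples = seconds × 0.5; full windows = whole part of (seconds / 512).

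| Recording | Seconds | Samples | Full windows |
|---|---|---|---|
| Heat hyperaemia, per site | 120 + 300 = 420 | 210 | 0 |
| Heat hyperaemia, upper limit per site | 900 / 2 = 450 | 225 | 0 |
| Baseline | 600 | 300 | 1 |
| Reactive hyperaemia | 1800 | 900 | 3 |
| Overlay load | 2400 | 1200 | 4 |

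The heat recording is short by 256 − 210 = 46 samples (92 s), or 46 / 256 = 18% of a window. At the upper limit it is still 512 − 450 = 62 s short. The mismatch is real for this recording and absent for the three used in the aims.

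**What would padding do?** With a Hann window and zeros added to reach 256 samples, the two-minute baseline carries 2.8%, 11.2% or 27.3% of the squared window weight, with padding at the end, split evenly or at the start. The choice would matter if such a spectrum were reported.

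**Does the plan call for such a spectrum?** The heat parameters in section 9.0 (peaks, times to peaks, area) all come from the fitted curve. Method 2 lists no parameters and no recordings. The hypotheses in section 3.0 concern interface pressure, skin blood flow under load and reactive hyperaemia. The tests in section 12.0 match them. None uses heat hyperaemia or a spectral quantity.

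**The AP cycle.** A 2400 s load period gives 1200 − 256 + 1 = 945 window positions. Across them, the larger single-phase share of squared weight runs from 50% to 97%, mean 80%: blurred, but not inseparable. Any figure for leakage of the cycle into slow bins needs an assumed waveform. If flow followed a square wave, 61–65% of the non-zero-frequency power would fall in the first bin and about 93% at or below 6 × 0.00195 = 0.0117 Hz. These shares describe the assumed wave. The documents give no means of finding its size relative to the rest of the signal.

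**The case for a change.** The best case for a change is that the scope really is unstated and would be cheap to state. The general sentence in section 9.0 excludes nothing. That heat hyperaemia is named only under curve fitting is weak evidence that it is left out of method 2, because reactive hyperaemia is also named only there. Section 2.0 adds heat hyperaemia to learn about vascular control, and method 2 is meant to examine control mechanisms, so the purposes match. The cited publication may settle scope and padding, but it is not part of the documents, and the recording length and AP cycle are set in this protocol. One paragraph and a script parameter would close the gap without new data.

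Much of this stands. The text does not say which recordings enter the spectrogram, and a reader cannot exclude the inclusive reading. What does not stand is that anything planned depends on it. The mismatch shows itself as soon as the window is applied to a 420 s recording, and the analyst can then keep heat hyperaemia to the time-domain parameters already listed, or shorten the window, after the data are collected. On the AP cycle, the plan names no contrast of high with low phases and no slow-band comparison of overlays. Flow driven by the cycle is also part of the overlay effect under study, so a rule against interpreting those bins would be a debatable choice resting on an assumed waveform.

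**Conclusion.** The arithmetic is right: the window exceeds the heat recording by 92 s (62 s at the longest), and no full window fits. It does not show an error in the plan. The 512 s figure is coherent at 0.5 Hz and suits the 600, 1800 and 2400 s recordings. Section 9.0 can reasonably be read as keeping heat hyperaemia in the time domain. On the wider reading, the missing scope or padding rule is a gap that analysts fill sensibly. No aim, hypothesis or planned paired t-test is affected, so no change follows.

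This rests on two conditions: that the stated 512 s reflects the rate actually used for the spectrogram, and that spectral results stay descriptive, as section 12.0 implies by naming none. If a heat-hyperaemia spectrum or a slow-band comparison of overlays were later reported as a finding, the window and padding used would need to be given with it.
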